4.1.8 Abacavir Hypersensitivity Reaction

Participants known to carry HLA-B*5701 must not receive abacavir. Participants for whom abacavir will be prescribed must be tested for the HLA-B*5701 allele; only those who are negative for the allele may be prescribed abacavir. In any participant treated with abacavir, the clinical diagnosis of suspected hypersensitivity reaction remains a clinical diagnostic decision. Even in the absence of the HLA-B*5701 allele, it is important to discontinue abacavir permanently and not re-challenge with abacavir if a hypersensitivity reaction cannot be ruled out on clinical grounds, due to the potential for a severe or even fatal reaction. Suspected cases of abacavir hypersensitivity of any severity (grade) must be reported in an expedited manner.

4.1.9 Resistance Testing

When initiating ART in either treatment group, resistance testing may be helpful to guide therapy changes; national or local treatment guidelines should be consulted.^{37,38} Additional information is provided in [Appendix F](#).

The decision to do resistance testing immediately prior to initiating ART should consider: (1) the regimen to be prescribed; (2) availability of previous resistance tests (e.g., closer to the time of seroconversion); and (3) risk of having transmitted drug resistance based on local data.

At each follow-up visit, the results of any locally obtained resistance testing will be recorded.

Plasma specimens will also be stored at baseline, 1 month, 4 months, and every 4 months thereafter for possible resistance testing. In addition, plasma specimens will also be collected from participants each time the ART regimen is switched or stopped due to an elevated HIV RNA level (or presence of resistance mutations). On a periodic basis, genotypic resistance testing may be performed on a sample of stored plasma specimens to assess prevalence of drug-related mutations.

Real-time resistance testing will not be provided as part of the START protocol.

4.1.10 Management of Virological Failure

If a participant experiences virological failure on any ART regimen, local guidelines should be followed to select antiretroviral drugs that will fully suppress HIV replication. Clinicians should consider the full spectrum of available and qualifying drugs.

In cases of multiple virological failures, participant adherence, the number of potential drug options available, and the risks and benefit of ART should be considered. For these participants, the use of drugs through expanded-access programs is permitted. There are no restrictions on use of ancillary therapies for HIV or use of other concomitant medications.

4.1.11 Discontinuation of ART

Treatment half-lives of the drugs taken should be considered any time ART is discontinued for any reason (e.g., for toxicity, intercurrent illness, elective surgery). In general, discontinuation of ART is not recommended, but it is recognized that there may be circumstances when it occurs. Differential half-lives of antiretroviral agents may have therapeutic implications for interruptions in therapy, particularly when participants are maximally suppressed. For instance, the prolonged half-life of the non-nucleoside reverse transcriptase inhibitors (NNRTIs) (efavirenz and nevirapine) could lead to unintentional monotherapy for a short period of time if all components of a potent NNRTI-containing regimen are discontinued at the same time. This may be even more significant in some intracellular reservoirs where the half-life of the NNRTIs may be even longer. The implications of these pharmacokinetic phenomena are unclear;

however, one small study that evaluated a 4-week interruption versus continuous therapy reported the emergence of resistance in five participants in the intermittent arm.³⁹ In SMART, among patients in the DC group taking an NNRTI and with an HIV RNA level ≤ 400 copies/mL at entry, those who interrupted all antiretroviral drugs simultaneously as compared to stopping ART drugs in a staggered manner or after replacing the NNRTI with another drug were less likely to achieve re-suppression when re-starting the NNRTI regimen. There was also a trend for more NNRTI mutations to develop when a simultaneous interruption strategy was used.⁴⁰

4.1.12 Documentation of Reasons for Initiation or Change in ART

Whenever ART is first initiated, and every time ART is changed for participants in either group (including discontinuation and subsequent re-initiation), the relevant information must be reported on the appropriate case report form. The reason(s) for (re)initiation, change or discontinuation of ART, including treatment-limiting toxicities, will also be recorded on the case report form.

4.1.13 Use of Drugs for Prophylaxis for Opportunistic Diseases

Just as for ART, local clinical practice guidelines should be consulted regarding choice of agents for prophylaxis for opportunistic diseases, if and when such prophylaxis is indicated.

4.1.14 Provision of Antiretroviral Drugs at Study Completion

Once the active follow-up phase of START has been completed, ART will be obtained by prescription from the participant's clinician. It is anticipated that at the end of START a closeout period of approximately 6 months will be required to complete all data collection. During this time period, ART from the INSIGHT Central ART Repository may be used, and sites will be expected to transition all participants to other sources of ART. During this time period adverse events will continue to be reported. Stopping ART is not recommended. All participating sites must have a plan for providing ART to participants at the end of the study.

4.2 CD4+ Cell Count and Viral Load Monitoring

CD4+ cell counts should be performed by laboratories that participate in proficiency testing programs.

Participants may be monitored more closely than data collection for this protocol requires. The frequency of non-study visits and measurements of CD4+ cell count and viral load will depend on the participant's clinical status and recent CD4+ cell count and viral load status. CD4+ counts can sometimes decline rapidly. Thus, for participants in the deferred group, it is important to monitor their CD4+ counts closely and begin preparing them to begin ART once the CD4+ count declines to < 400 cells/mm³, in particular in participants with higher viral loads. ART should be initiated as recommended in section 3.7.1.

Participants randomized to the deferred arm whose CD4+ cell count drops to less than 350 cells/mm³ should have a repeat CD4+ measurement within 4 weeks to confirm this decrease. If the decrease is confirmed, the clinician should prescribe ART to be started by the participant as soon as possible within 4 weeks of confirmation of the decrease. In some cases, clinicians may choose to initiate ART before these criteria are met. Deviations from the protocol-specified criteria must be reported on a case report form.

Following the initiation of ART (immediately following randomization for the early ART arm or later in follow-up for the deferred arm), local guidelines should be followed for monitoring CD4+ cell count and HIV RNA levels. Most guidelines recommend that HIV RNA level be measured within 2-8 weeks after ART initiation. For participants on stable ART, HIV RNA levels should be determined every 3-4 months. For START, HIV RNA levels are required at least every 4 months.

4.3 Pregnancy and Breastfeeding

Women are not eligible for enrollment into the study during their pregnancy or while they are breastfeeding. However, they may be randomized after delivery if they are ART naive. World Health Organization (WHO) guidelines recommend that women with HIV infection avoid breastfeeding “when replacement feeding is acceptable, feasible, affordable, sustainable and safe.”⁴¹

For women of child-bearing potential, a serum or urine pregnancy test must be performed before randomization and whenever pregnancy is suspected. For women to be prescribed efavirenz, a pregnancy test should be performed as close to the start of treatment as feasible and no more than 14 days beforehand.

Women in either treatment group who become pregnant during follow-up should be managed according to principles found in national^{42,43} and international guidelines.^{41, 33} This requires a careful assessment of the mother’s HIV disease stage, antiretroviral experience, gestational age, and the risks and benefits of specific antiretroviral regimens or other interventions.

Pregnant women are still considered active study participants and will be counted in their assigned randomized group for primary analyses. After delivery and breastfeeding, women will continue their assigned treatment strategy. Women will be counseled concerning breastfeeding based on national and/or WHO guidelines. Outcomes of pregnancy will be reported.

Study staff are encouraged to register pregnancies that occur on study prospectively with *The Antiretroviral Pregnancy Registry*. A link to this registry is available on the INSIGHT website (see [Appendix H.](#))

4.4 HIV Transmission Counseling

All participants should receive counseling regarding prevention of HIV transmission to others as indicated.

4.5 Study Withdrawal

Participants may withdraw from the study at any time at their request and resume participation at any time upon re-consent. A participant may be withdrawn if:

- He/she relocates and data can no longer be collected.
- He/she is imprisoned, or involuntarily incarcerated for medical reasons. In this case, no data will be collected during the imprisonment or involuntary incarceration. However, once released from imprisonment or involuntary incarceration, an individual may resume participation in the group to which he or she was originally assigned upon re-consent.
- The study is discontinued.

All participants should otherwise be followed according to protocol. Even if a participant chooses not to adhere to the treatment assignment or data collection schedule, every effort should be made to follow participants for the primary composite endpoint until the end of the study.

4.6 Co-enrollment in Other Studies

There are no restrictions on co-enrollment in other studies as long as co-enrollment does not interfere with a participant's assigned treatment strategy in START.

5 Evaluation

5.1 Data Analysis

The primary analysis will be by intention to treat, comparing the early and deferred groups. Thus, all participants will be included in the primary treatment comparison, irrespective of whether they adhered to their assigned ART strategy. Time-to-event methods, including stratified log-rank tests, proportional hazards regression analysis, and Kaplan-Meier cumulative event curves, will be used to summarize the primary endpoint (i.e., time to the first event) and major secondary outcomes.⁴⁴ As part of these analyses, the proportionality of the hazards over time will be assessed. The primary analysis will be based on a Cox model with a single indicator for treatment group and with strata corresponding to geographic region (North America, South America, Europe, Australasia, and Africa).

Subgroup analyses for the primary endpoint and major secondary outcomes will be performed to determine whether the treatment effect (early versus deferred) differs qualitatively across various baseline-defined subgroups. Subgroup analyses will be performed by age, gender, race/ethnicity, geographic region, the presence of risk factors for serious non-AIDS conditions, baseline CD4+ cell count, baseline HIV RNA level, calendar date of enrollment in order to assess the effect of different treatment patterns that may emerge, and the ART regimen prespecified at the time of randomization. The latter subgroup analysis will permit evaluation of major outcomes for those who receive an NNRTI-based treatment as immediate ART versus deferral of ART (compared to those who would have been given an NNRTI-based regimen immediately had they been randomly assigned to immediate ART), and for those who receive a protease inhibitor (PI)-based regimen as immediate treatment versus deferral. The consistency of the treatment difference across participating countries will also be assessed. An overall test of heterogeneity will provide evidence of whether the magnitude of the treatment difference varies across baseline subgroups.

The goal of the study is to enroll participants at variable risk of serious non-AIDS diseases. Thus, the characteristics of participants enrolled will be closely monitored to ensure good representation of participants with major risk factors for serious non-AIDS conditions. Descriptive analyses will also be carried out summarizing ART regimens used by the early and deferred groups. These analyses will be carried out by geographic region and by calendar period of enrollment and follow-up. The initial ART regimen used will be compared to the regimen specified prior to randomization.

The CD4+ inclusion criteria for the study and the CD4+ count threshold for initiation of ART in the deferred strategy were defined to result in two treatment groups that differ substantially in terms of ART exposure, and consequently, HIV RNA level and CD4+ cell count. As part of the ongoing monitoring of this study, time to initiation of ART in the deferred group will be monitored and HIV RNA levels and CD4+ cell counts will be compared for the early and deferred groups. Initiations of ART in the deferred group that are not in keeping with the protocol will be closely monitored. Likewise,

discontinuation of ART in the early and deferred groups will be closely monitored. Kaplan-Meier life-table methods will be used to estimate the cumulative percent of participants in the deferred group who initiate therapy after different periods of follow-up. Follow-up levels of HIV RNA and CD4+ count will be summarized in a number of ways. Follow-up time spent in various categories will be compared. Longitudinal measurements of viral load and CD4+ cell count will be summarized using measured levels (or log transformed) and using repeated binary assessments (e.g., viral load below 50 copies/mL).

In addition, within each treatment group a number of analyses aimed at predicting changes in CD4+ cell count, viral load, and clinical responses will be carried out. These will include analyses of predictors of HIV RNA suppression and CD4+ cell count increases following initiation of ART.

Analyses aimed at understanding whether differences in CD4+ cell count and HIV RNA levels explain differences in the primary endpoint and its components will be carried out. These models will employ Poisson regression models and Cox models with time-varying covariates. Account will be taken of the measurement error associated with CD4+ count and HIV RNA that could attenuate associations with risk of the primary endpoint.

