3.5 Sample Size and Statistical Considerations

It is estimated that 4,000 participants will be required to reliably address the primary study question. This is based on estimates of the expected event rates in the early and deferred ART groups using data from the CASCADE Collaboration and UK CHIC³⁴ with computer simulations that account for the distribution of CD4+ cell counts projected for START. These estimates and other assumptions used in calculating sample size are described in detail in [Appendix G](#) and summarized below:

- a. The primary analysis will be intention to treat using a Cox model with a single indicator for treatment group and with strata corresponding to geographic regions (North America, South America, Europe, Australasia, and Africa).
- b. Type I error is 0.05 (2-sided) and power = 0.90. Power was set at 90% for the primary endpoint, in part, to ensure that there would be adequate power to address the components of the composite endpoint, non-AIDS and fatal AIDS or non-fatal AIDS*.
- c. Participants will be enrolled over a 3-year period (2 additional years after the one year pilot phase) and followed for a minimum of 3 years resulting in an average follow-up of 4.5 years and a total study duration of 6 years.
- d. The CD4+ cell count at entry will be between 501 and 600 cells/mm³ for 70% of participants, between 601 and 700 cells/mm³ for 20%, and > 700 cells/mm³ for 10%.
- e. In the deferred ART group, the rate of the primary endpoint is 2.8 per 100 person years over the follow-up period. Non-AIDS events will be four times more common than non-AIDS deaths, and approximately 35% of reported AIDS events and 10% of

reported non-AIDS events will not meet probable or confirmed criteria (i.e., the criteria that have to be achieved to count the reported event as an endpoint). In SMART, the rates of confirmed or probable fatal AIDS or non-fatal AIDS* and of serious non-AIDS, as defined in START, were 0.4 and 2.0 per 100 person-years, respectively, in the VS group.³⁵

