- f. Based on the computer simulations described in [Appendix G](#), early ART is predicted to reduce the primary endpoint rate by 28.8% compared to deferred ART. This reduction in the hazard assumes: (1) AIDS* events represent 23% of the events in the deferred arm, and early ART will reduce this hazard by 43%; and (2) non-AIDS events and deaths not attributable to AIDS will represent 77% of events in the deferred ART group, and early ART will reduce this hazard by 24%. The smaller percentage risk reduction anticipated for non-AIDS events and deaths not attributable to AIDS takes into account that some of the deaths will be due to causes that are unrelated to HIV and ART. For example, 18% of deaths in SMART were due to substance abuse, accidents or violence.¹¹
- g. The estimated treatment differences take into account likely levels of adherence to the early ART strategy (e.g., participants followed in CASCADE who started ART were considered “on ART” irrespective of adherence or future discontinuation of their ART).
- h. Adherence to the deferred strategy was also considered. It was assumed that 70% of participants would adhere to the deferral CD4+ threshold of 350 cells/mm³ and 30% would initiate ART earlier – 10% before the CD4+ declined to 400 cells/mm³ and 20% while the CD4+ was between 350 and 400 cells/mm³.
- i. A loss to follow-up rate of 2.7 per 100 person-years (equivalent to a 15% cumulative lost to follow-up after 6 years) is assumed.
- j. Based on these assumptions, 3,822 participants (1,911 participants in each treatment group) are required. The number of primary events required is 369.
- k. While many of the underlying assumptions are conservative, for some assumptions there is much uncertainty because of the absence of data (e.g., inadequate or no data on rates of non-AIDS morbidity). Considering this, a sample size of 4,000 participants (2,000 in each treatment group) and a target of 370 primary events has been established as the initial goal. This may be modified following sample size re-estimation.

Power was also estimated for the components of the primary endpoint. With the above assumptions, and with 4,000 participants and 370 primary events, power is 0.74 to detect a 43% reduction in the hazard of AIDS*, and power is 0.73 to detect a 24% reduction in the hazard of non-AIDS and deaths not attributable to AIDS.

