Older age is associated with an increased risk of each of these diseases. As HIV populations with access to ART age, these events will increase in absolute numbers. Smoking is an established risk factor for many diseases including cardiovascular, renal and liver disease and many cancers.¹⁸² For CVD, the major risk factors are blood cholesterol level, blood pressure, smoking, overweight/obesity, diets high in fat and cholesterol, and diabetes mellitus.^{183,184} These risk factors are additive in their effects on CVD risk, and for blood pressure and blood cholesterol, risk of a cardiovascular event is not restricted to those with hypertension or hypercholesterolemia. Risk equations for predicting long-term risk of CVD morbidity and mortality have been developed taking into account actual levels of blood pressure and blood cholesterol.¹⁸⁵

Risk factors for renal disease are similar to those for CVD. Blood pressure and diabetes mellitus are major risk factors. Smoking and elevated blood cholesterol are also associated with an increased risk of renal disease.¹⁸⁶ African-Americans have a greater risk of kidney disease than other race groups.¹⁸⁷ Traces of protein on a casual urine dipstick and above average creatinine levels (e.g., 1.5-2.0 mg/dl) have been associated with long-term risk of ESRD.¹⁸⁸ The National Kidney Foundation in the United States has adopted a new classification scheme for chronic kidney disease as an estimated glomerular filtration rate (eGFR) < 60 mL/min per 1.73 m² or proteinuria.¹⁸⁹ Creatinine will be measured in START at baseline and all follow-up examinations in the first year and annually afterward in order to estimate GFR. The simplified Modification of Diet in Renal Disease equation will be used.³⁶

Chronic hepatitis C infection is a major risk for cirrhosis, hepatocellular carcinoma, and death from liver disease.^{190,191} The association between co-infection and risk of AIDS or death has not been consistent in different studies.^{191,192,193} In SMART, approximately 15% of patients were co-infected with hepatitis C.¹¹ Risk of non-AIDS death was three- to fourfold higher among co-infected patients and the majority of these patients were co-infected with hepatitis C.¹³⁸ Chronic hepatitis B infection is associated with an increased risk of death from liver disease.¹⁵ However, co-infection with hepatitis B virus is expected to be less common in the target population for START because of the location of sites.

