- Main study consents (Appendices A-1 and A-7): Incorporated language regarding updated US guidelines in consents per Jan 2010 communication to investigators.
- Main study consents: Modified language to permit sites to use a single consent for the main study that includes permission to collect and store specimens. A separate consent for specimen storage is still available (Appendix A-2); its signature page has been updated.

- Genomics Substudy consent, “What do you have to do if you are in the Genomics Substudy?”: corrected error in amount of blood to be drawn (9 mL instead of 6 mL; 6 mL is the amount being *stored*).
- Other consents: Incorporated Clarification Memos in regard to malignancy specimen collection (Appendix A-3), Genomics substudy involuntary withdrawal (Appendix A-4), and contraceptive language in main study Concise consent (Appendix A-7).
- Appendix C (Time & Events Schedule): Removed substudy data collection items, as there are now substudies open which are not included in the main protocol document. A Time & Events Schedule which includes data collection items for all substudies will be maintained on the INSIGHT website in a format that will allow sites to download it and delete items for those substudies in which they are not participating.
- Appendix D: Deleted INSIGHT Executive Committee (no longer exists). Updated START protocol team membership.

Summary of additional changes to START protocol Version 2.0, dated 25 October 2010

1. References to international regulatory documents (Declaration of Helsinki, EU clinical trials directives) modified to refer to “current version” rather than a specific version that may have since been updated. (Clarification Memo, 17 February 2011)
2. As planned, the sample size was re-estimated before enrollment was completed. Section 5.3 is added to the protocol to detail the updated sample size and primary event target. The inclusion criterion for age is changed to 35 years or older after 4,000 participants are enrolled to increase the likelihood of primary endpoints. (Letter of Amendment 2, 14 February 2013)
3. To comply with changes in EU guidance and individual country laws, language is added requiring reporting of serious adverse events within 24 hours following investigator knowledge of the event, for sites in EU member states. (Letter of Amendment 2.1, 13 May 2013)

Analysis Plan Informed Consent Substudy (26 Oct 2013)

INSIGHT START

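### The primary Cox model is valid and meets its 90% power, but beyond region strata it uses no baseline prognostic covariate; prespecifying age would add a little power at almost no cost.

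*Supplement*

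**What the plan says.** Sections 3.5 (item a) and 5.1 of protocol Version 2.0 fix the primary analysis as intention to treat: "The primary analysis will be based on a Cox model with a single indicator for treatment group". Five geographic regions serve as stratification factors, and no other term enters. Age appears in the analysis only as a subgroup factor (3.2.2 item c and 5.1).

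Elsewhere the documents treat age as prognostic for the endpoint:

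- Section 3.5 item f plans that "non-AIDS events and deaths not attributable to AIDS will represent 77% of events" in the deferred arm.
- Appendix B, on risk factors for non-AIDS conditions, says: "Older age is associated with an increased risk of each of these diseases".
- The summary of additional changes to Version 2.0 (item 2) says: "The inclusion criterion for age is changed to 35 years or older after 4,000 participants are enrolled to increase the likelihood of primary endpoints".

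Age is known for everyone. It is an entry criterion (3.6.1), and demographics are part of baseline screening (3.7.3). Smoking, hepatitis status and HIV RNA are also collected before randomization.

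**The concern.** The trial deliberately enrols people at widely differing baseline risk (2.3.2, 3.6), measures that risk, and then leaves it out of the primary model except for region. In a Cox model, omitting a strong predictor of the outcome pulls the treatment hazard ratio slightly towards 1, even under perfect randomization, and so lowers the test statistic. Including the predictor restores that loss without more participants, events or follow-up. At stake is a modest amount of power in a trial whose event rates the protocol itself calls uncertain.

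**Working it through.** **Inputs from the documents.** Section 3.5: "Type I error is 0.05 (2-sided) and power = 0.90"; "early ART is predicted to reduce the primary endpoint rate by 28.8% compared to deferred ART", i.e. a hazard ratio (HR) of 0.712; "In the deferred ART group, the rate of the primary endpoint is 2.8 per 100 person years" (2.81 in Table G-3); loss to follow-up 2.7 per 100 person-years; 3 years of accrual and 6 years in total; 369 events required with 3,822 participants; targets of 370 events and 4,000 participants. Allocation is 1:1 (3.4).

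**Step 1: reproduce the plan's figure.**

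- Schoenfeld: 4(1.960 + 1.282)² / (ln 0.712)² = 42.03 / 0.1154, giving 365 events.
- Freedman: (1.712 / 0.288)² × (1.960 + 1.282)² = 35.34 × 10.51, giving 372 events.
- The stated 369 lies between them. With constant hazards, 3,822 participants yield about 368 expected events.
- Power of the planned model at 370 events: Φ(½√370 × |ln 0.712| − 1.960) = Φ(3.267 − 1.960) = 90.4%.

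The planned analysis therefore delivers what it promises.

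**Step 2: what age adjustment adds.** The documents give neither an age hazard ratio nor an age distribution, so the HR per SD of age is an assumption and is shown as a range. For each value, 20,000 trials of 4,000 participants were simulated with a normally distributed age, a log-linear age effect, constant hazards, a deferred-arm rate of about 2.81 per 100 person-years, a treatment HR of 0.712 conditional on age, and the loss and follow-up above. Each trial was analysed twice, with treatment alone and with treatment plus age. Region strata were not simulated.

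| Assumed age HR per SD | Mean events | Power, treatment only | Power, with age | Gain (points) | HR, treatment only | HR, with age | Relative efficiency |
|---|---|---|---|---|---|---|---|
| 1.25 | 383.9 | 90.8% | 90.8% | 0.0 | 0.712 | 0.711 | 1.006 |
| 1.5 | 381.4 | 90.0% | 90.5% | 0.4 | 0.714 | 0.712 | 1.019 |
| 1.75 | 377.8 | 89.3% | 90.6% | 1.3 | 0.716 | 0.712 | 1.037 |
| 2.0 | 373.3 | 89.1% | 90.8% | 1.7 | 0.718 | 0.711 | 1.061 |
| 2.5 | 362.6 | 86.0% | 89.8% | 3.9 | 0.725 | 0.712 | 1.117 |

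The Monte Carlo standard error of each gain is 0.07 to 0.18 points. Comparisons should be made within a row, because mean events also fall down the table. On 370 events, 370 × (relative efficiency − 1) is about 2, 7, 14, 23 and 43 extra events.

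**Step 3: where the gain comes from.** At an age HR of 2.0 the mean standard error is 0.1050 without age and 0.1051 with it, so precision does not improve. The log HR moves from ln 0.7178 = −0.3316 to ln 0.7106 = −0.3416, a ratio of 1.030, and 1.030² ≈ 1.06, which is the whole relative efficiency. The two hazard ratios differ by 0.7178 / 0.7106 − 1 = 1.0%; at an age HR of 2.5 the difference is 0.7252 / 0.7119 − 1 = 1.9%.

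**Step 4: is any covariate in this range?** Appendix B reports that about 15% of SMART participants had hepatitis C, and that non-AIDS death was three- to fourfold higher in co-infected patients. Treated as one binary factor, the SD of the log hazard is ln 3 × √(0.15 × 0.85) = 0.39 to ln 4 × √(0.15 × 0.85) = 0.50. For comparison, ln 1.5 = 0.41 and ln 1.75 = 0.56. This is rough: it concerns death rather than the composite, another trial's population, and co-infection with either virus.

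**The case against.** The strongest case against is that nothing is broken. A treatment-only model stratified by region is a standard intention-to-treat analysis, the sample size was built for it, and it meets its target. That stands.

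The gain is also not recovered precision. It is the move to a hazard ratio conditional on age, so a gain in the test statistic and a wholly unchanged estimand cannot both be claimed. That stands too, although at an event risk of about 370 / 4,000 = 9% the change in estimand is very small.

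A third argument is that the simulation takes 0.712 as the conditional HR, whereas the protocol may mean the unadjusted one. In that case the planned model keeps its 90.4%, but adjustment still adds to it. At an age HR of 2.0, Φ(3.267 × √1.0613 − 1.960) = Φ(1.406) = 92.0%, a gain of 1.6 points; at 2.5 it is Φ(1.493) = 93.2%, a gain of 2.8. The choice changes the baseline, and the gain at the extreme, but not the conclusion.

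The strength of age is unknown. A reader might infer from the change to a minimum age of 35 that age is strongly prognostic. The change summary shows only the direction in which the sponsor expects age to act. It applies after 4,000 participants, and it narrows the age range of later entrants.

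Finally, Section 5.3, which holds the re-estimated sample size and event target, is mentioned in the change summary but its text is not shown. No analysis plan for the main trial is shown either. The 370 events used here may be superseded, and an age-adjusted supportive analysis may already exist. The primary model, however, is explicit in 3.5 and 5.1.

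**Conclusion.** The point holds as a minor efficiency suggestion. For an assumed age HR of 1.25 to 2.0 per SD the power gain is about 0 to 1.7 points. It approaches 4 points only at 2.5 per SD, which no figure in the documents supports for age alone. These sizes rest on constant hazards, a log-linear age effect and no region strata in the simulation.

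A reader might go further and infer that the primary analysis is underpowered or wrong, that it accounts for nothing but treatment, or that adjustment is free power. The documents support none of these: power is 90.4% at 370 events, region is already a stratification factor, and the adjusted hazard ratio answers a very slightly different question.

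**What to change.** Before unblinding, and decided by team members who remain blinded under 5.2, amend 3.5 item a and 5.1 so that the primary Cox model contains treatment and continuous baseline age, stratified by the five regions. A short fixed list could be added, such as smoking, hepatitis co-infection and log10 HIV RNA. Keep the region-stratified treatment-only model as a supportive analysis.

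State in 5.2 that the same statistic is used against the O'Brien-Fleming-type boundary, for the component consistency guideline and for conditional power. Check Section 5.3 for consistency.

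The cost is a few sentences across 3.5, 5.1 and 5.2, with no additional data, participants or follow-up. The reported hazard ratio becomes conditional on age, differing from the unadjusted one by about 1% at an age HR of 2 per SD; reporting both side by side settles that.
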